5.14.3 POTENTIAL BENEFITS

In general, patients may not experience any direct benefits.

Based on the performance of other cleared pedicle screw systems that have successfully relieved symptoms of degenerative disc disease, and clinical experience with the investigational device outside the United States, there is reason to believe that the CarboClear Pedicle Screw System could also relieve DDD symptoms.

5.14.4 ADVERSE EVENTS

5.14.4.1 Definitions

Adverse Event (AE)

Any untoward medical occurrence, unintended disease or injury, or untoward clinical signs in subjects, users or other persons, whether or not related to the investigational medical device (including events related to the investigational medical device; and events related to the procedures involved).

Serious Adverse Event

Defined as one of the following events:

- a. Death;
- b. Serious deterioration in the health of the subject, that either resulted in:
 - a life-threatening illness or injury, or
 - a permanent impairment of a body structure or a body function, or
 - in-patient or prolonged hospitalization, or
 - medical or surgical intervention to prevent life-threatening illness or injury or permanent impairment to a body structure or a body function,
- c. Event that led to fetal distress, fetal death or a congenital abnormality or birth defect.
- Note: Planned hospitalization for a pre-existing condition, or a procedure required by the protocol, without serious deterioration in health, is not considered a serious adverse event.

Adverse Device Effect

Adverse event related to the use of an investigational medical device (including adverse events resulting from insufficient or inadequate instructions for use, deployment, implantation, installation, or operation, or any malfunction of the investigational medical device, and any event resulting from use error or from intentional misuse of the investigational medical device).

Serious Adverse Device Effect (SADE)

Adverse device effect that has resulted in any of the consequences characteristic of a serious adverse event.

Device Deficiency

Inadequacy of a medical device with respect to its identity, quality, durability, reliability, safety or performance (including malfunctions, use errors, and inadequate labeling).

Unanticipated Adverse Device Effect

Unanticipated adverse device effect means any serious adverse effect on health or safety or any life-threatening problem or death caused by, or associated with, a device, if that effect, problem, or death was not previously identified in nature, severity, or degree of incidence in the investigational plan or application (including a supplementary plan or application), or any other unanticipated serious problem associated with a device that relates to the rights, safety, or welfare of subjects.

5.14.4.2 Assessing and Reporting of Adverse Events

All adverse events, adverse device effects and device deficiencies (collectively: "Adverse Events") will be documented using the relevant Adverse Events Report Forms. In addition, each subject will be questioned about Adverse Events at each follow-up visit. Adverse Events discovered during a routine follow-up will be documented additionally on the relevant follow-up CRF.

Adverse Events occurring during the study will be treated by established standards of care that will protect the life and health of the study subjects.

Signs and symptoms of each Adverse Event should be described in detail and include start and stop dates, intensity, correlation with investigational device, action taken and outcome.

The Investigator shall evaluate and document the following:

- 1. whether any Adverse Events have occurred;
- 2. the nature of the event;
- 3. date of Adverse Event onset and duration;
- 4. seriousness of the event (serious, moderate, mild/minor);
- relation to the investigational device (not related, possibly related, definitely related);
- 6. Adverse Event outcome and the course taken to reach the outcome.

The report of AEs based on specific type of event will be classified according to the following AE terms, listed in the table below, and in accordance with FDA list of risks applicable for pedicle screw spinal systems (FDA's Executive Summary, Table 11).

ADEVERSE EVENTS
Implant Malposition
Implant Loosening
Device Breakage
Construct Disassembly
Bone Fracture
Graft Settling/Displacement
Loss of Correction
Pseudoarthrosis
Bleeding/Vascular Injury
Neurologic Injury
Back/Leg Pain (Radiculopathy)
Dural Tear/CSF Leak
Wound problems
Infection/Sepsis
Skin Irritation
Cardiac
Respiratory
Gastrointestinal
Reoperation/Revision
Death

In addition, as per the FDA recommendation, the adverse events will be further classified according to the following Adverse Events table (as applicable to this study, *e.g.*, no control group):

	Surg t Discl		to W	harge /eek 6	Wee to Mo		Mon 3 to		Mor 6 to		Moi 12 te		Mon 18 to		Investiga grou		Contr Grou	-
Adverse Event Category	Ι	С	Ι	C	Ι	С	Ι	C	Ι	С	Ι	C	Ι	С	#Subjects (% of xx)	Total Events	#Subjects (% of xx)	Total Events
All Adverse Events ¹															x (x %)	x	x (x %)	x
(Includes Perioperative Systemic E	vonta	Polot	-	perativ		-	-		-	-				road	ura (initial a	raubaaau	ant) at the inc	lov or
(includes renoperative Systemic E	vents	Kelau		uie Ope	lauve		djacer	-		J wee	KS 01	any sp	nne p	loceu	ure (initial of	subsequ	ent) at the mo	lex of
Implant (Total)																		
Breakage																		
Loosening																		
Migration																		
Malposition																		
Subsidence																		
Lumbar Spinal Event Target Level (Total)																		
Spinous Process Bone Erosion																		
Spinous Process Bone Reactive Change / Sclerosis																		

	t	gery 0 harge		harge 'eek 6		ek 6 onth 3	Mon 3 to		Mor 6 to		Moi 12 te		Mor 18 te		Investiga grou		Contr Grou	
Adverse Event Category	Ι	C	Ι	С	Ι	C	Ι	C	Ι	C	Ι	C	Ι	С	#Subjects (% of xx)	Total Events	#Subjects (% of xx)	Total Events
Spinous Process Fracture																		
Facet Joint Degenerative Changes (Weishaupt)																		
Other (please specify in footnote)£																		
Lumbar Spinal Event Adjacent Contiguous Level																		
Lumbar Spinal Event Adjacent																		
Non-Contiguous Level																		
Nonoperative Control Group Event																		
Nonunion (pseudarthrosis)																		
T. 4.1	1		1			Intra	opera	tive	Even	ts	1							
Total																		
Anatomic/Technical Difficulty																		
Lumbar –Initial Surgery																		

	t	gery o harge		harge 'eek 6	Wee to Mo		Mon 3 to		Mor 6 to			nths o 18	Moi 18 te		Investiga grou		Contr Grou	
Adverse Event Category	Ι	C	Ι	С	Ι	C	Ι	C	Ι	C	Ι	C	Ι	С	#Subjects (% of xx)	Total Events	#Subjects (% of xx)	Total Events
Lumbar – Subsequent Surgery																		
Device Unable to be Implanted																		
Intraoperative Device Revision																		
Dural Tear/Leakage																		
Intraoperative Vascular Injury																		
Anesthesia, Airway, Ventilation																		
Visceral Injury																		
Intraoperative Neurologic Injury																		
Intraoperative hypotension																		
Blood transfusion																		
Excessive blood loss																		
Major allergic reaction																		
Other (please specify in footnote)																		
		P	l eriopo	erative	Syster	nic Ev	ents (Occ	l urrin	l g ≤ 6v	veeks	s of op	erati	on)				
Total					•	1				 		-				1		
Deep vein thrombosis																		

	t	gery o 1arge	to W	harge 'eek 6	Wee to Mo		Mon 3 to		Mor 6 to		Mon 12 to		Mor 18 te		Investiga grou		Contr Grou	•-
Adverse Event Category	Ι	C	Ι	С	Ι	C	Ι	С	Ι	С	Ι	С	Ι	С	#Subjects (% of xx)	Total Events	#Subjects (% of xx)	Total Events
Pulmonary embolism																		
Retrograde Ejaculation																		
Anesthesia, Airway, Ventilation																		
Cardiac arrest/failure/arrhythmia																		
Myocardial infarction																		
Dysphagia																		
Dysphonia																		
Gastrointestinal bleeding																		
Pneumonia																		
Pressure sores																		
Urinary tract infection																		
CSF leak/meningocele																		
Sepsis unrelated to operative site																		
Other (please specify in footnote)																		
Post-	Surgi	cal Sp	oinal l	Injectio	ons / N	eedle	Based	Pro	cedu	res /R	hizot	omies	s / Spi	nal S	timulators			
Total																		
Epidural																		
Nerve root block																		
Facet Joint injection																		
Medial branch block																		
Sacroiliac injection																		
Trigger point																		
Rhizotomies																		

	Surg te Disch		to W	harge eek 6	Wee to Mo		Mon 3 to		Mor 6 to		Moi 12 te		Mon 18 te		Investiga grou		Contr Grou	-
Adverse Event Category	Ι	С	Ι	С	Ι	С	Ι	С	Ι	С	Ι	С	Ι	С	#Subjects (% of xx)	Total Events	#Subjects (% of xx)	Total Events
Spinal Stimulators																		
Other (please specify in footnote)																		
				Inc	ision-F	Related	l, Nor	n-Inf	ectiou	ıs (Lu	mba	r)						
Total																		
Posterior Lumbar																		
Study Surgical Incision																		
Dehiscence																		
Hematoma																		
Hematoma Evacuation																		
CSF Leakage																		
Posterior Lumbar Non-Study																		
Incision (Specify AE type)																-		
	8	1	1			1	Infe	ction		1	-	1	-	1		1	[1
Total																		
Superficial Wound – Posterior																		
Lumbar Study Incision																		
Deep Wound – Posterior Lumbar Study Incision																		
Visceral / Organ space (Index level)																		
Superficial Wound – Posterior																		
Lumbar Non-Study Incision																		
Deep Wound – Posterior Lumbar																		

	t	gery o narge	to W	harge /eek 6	Wee to Mo		Mon 3 to		Mor 6 to			nths o 18	Moi 18 te		Investiga grou		Contr Grou	
Adverse Event Category	Ι	C	Ι	C	Ι	С	Ι	C	Ι	С	Ι	C	Ι	C	#Subjects (% of xx)	Total Events	#Subjects (% of xx)	Total Events
Non-Study Incision																		
Visceral / Organ space (Non-Index Spinal level)																		
Other (i.e., cellulitis, erythema)																		
				Subs	eauen	t Surg	ical I	nter	ventio	ons (L	լ աmb	ar)						
Total			1		- 1					(
Reoperation: Index level																		
Reoperation: Adjacent Contiguous Level																		
Reoperation: Index level and																		
Adjacent Contiguous Level																		
Reoperation: Adjacent Non- Contiguous Level																		
						N	eurol	logic	al†				-					
Neurological																		
Total (Upper extremity)		ļ																
Upper Extremity – Sensory																		

	t	gery zo harge	to W	harge /eek 6		ek 6 onth 3	Mor 3 to		Mor 6 to		Moi 12 t	nths o 18	Moi 18 te		Investiga grou	р	Contr Grou	ıp
Adverse Event Category	Ι	C	Ι	C	Ι	C	Ι	С	Ι	C	Ι	C	Ι	C	#Subjects (% of xx)		#Subjects (% of xx)	Total Events
Upper Extremity – Motor																		
Upper Extremity – Reflex																		
Total (Lower extremity)																		
Lower Extremity – Sensory																		
Lower Extremity – Motor																		
Lower Extremity – Reflex																		
Spinal Cord / Cauda Equina Disturbance																		
Upper extremity nerve compression (i.e. carpal tunnel)																		
Subjective*																		
Non-specific or Other**																		
																		+
		 	•	Pa	in Eve	ents Co	Pain I onside			ine-R	elate	d	•	1				
Cervical Spine/Upper Extremity			1															
Pain (Total)																		
Cervical Pain (Cervical Region)																		1
Upper Extremity Pain													Ī					
Combined Cervical and Upper Extremity Pain	Ī																	
Thoracic Pain (Thoracic Region)																		

	t	gery 0 harge	to W	harge /eek 6		ek 6 onth 3	Mor 3 to		Mor 6 to		Moi 12 t		Moi 18 te		Investiga grou	р	Contr Grou	ıp
Adverse Event Category	Ι	C	Ι	C	Ι	C	Ι	С	Ι	C	Ι	C	Ι	С	#Subjects (% of xx)		#Subjects (% of xx)	Total Events
Lumbar Spine/Lower Extremity Pain (Total)																		
Low Back Pain (Lumbar Region)																		1
Lower Extremity Pain																		
Combined Low Back and Lower Extremity Pain																		
	•	1	•			Other	(Non-	-Spir	nal) P	ain		1	•	1				1
Total																		
Upper Extremity																		
Torso/Mediastinal																		
Lower Extremity																		
Headache																		
Abdominal																		
Pelvic																		
Other (please specify in footnote)																		
			-			Muscu	ıloske	eleta	l Eve	nts								
Total																		
Cervical																		
Thoracic																		
Lumbar																		
Upper Extremity																		
Lower Extremity																		
Sacroiliac																		

	Sur; t Discl		to W	harge eek 6	Wee to Mo		Mon 3 to		Mor 6 to		Mor 12 to		Mon 18 to		Investiga grou		Contr Grou	•-
Adverse Event Category	Ι	С	Ι	С	Ι	С	Ι	С	Ι	С	Ι	С	Ι	С	#Subjects (% of xx)	Total Events	#Subjects (% of xx)	Total Events
Other (please specify in footnote)																		
System	ic Ev	ents (Total	Inclu	des Sys	stemic	Even	ts O	ccurr	ing V	Vithin	6 W	eeks (of Ind	ex Surgery)			
Total																		
Respiratory																		
Cardiac																		
Gastrointestinal																		
Infection (Systemic)																		
Cancer																		
Dermatologic																		
Urogenital																		
Ear, Nose, Throat																		
Hematologic																		
Endocrine																		
Hepatobiliary																		
Immunologic																		
Metabolism/Nutrition																		
Gynecologic																		
Opthalmologic																		
Psychological																		
Pregnancy																		
Surgical Procedure: Non-Spinal																		
Wound Infection (other f1spinal																		
region: thoracic, cervical)																		
Wound Infection (non-spine related																		

	-	gery o narge	to W	harge 'eek 6			Mon 3 to		Mor 6 to		Mon 12 to		Mor 18 to		Investiga grou		Contr Grou	-
Adverse Event Category	Ι	C	Ι	С	Ι	С	Ι	С	Ι	С	Ι	С	Ι	С	#Subjects (% of xx)	Total Events	#Subjects (% of xx)	Total Events
incision)																		
Incision-Related, Non-Infectious (other spinal region: thoracic, cervical)																		
Incision-Related, Non-Infectious (non-spine related incision)																		
Spinal Event Thoracic	1																	
Spinal Event Cervical																		
Other (please specify in footnote)																		
Death																		
Totals																		

Classification of Adverse Events by their seriousness and relationship to the investigational device shall be performed according to the following definitions.

Seriousness of Adverse Event

- Serious Adverse Event an undesirable event that is fatal or life-threatening, or serious deterioration in the patient health that results in disabling (permanent impairment) or which necessitates prolonged hospitalization or medical or surgical intervention to prevent said life-threatening illness/injury or permanent impairment. Examples of serious adverse events are nerve root injury leading to significant and permanent paralysis, and vascular damage to major vessel.
- Moderate Adverse Event an undesirable event that does not fall into any of the serious adverse event definitions, and that may cause non-severe deterioration in the patient health (without significant permanent harm); moderate adverse event may require medical or minimal invasive surgical intervention or prolonged hospitalization. Examples of moderate adverse events are seroma or hematoma that mandate drainage, or dehiscence mandating revision of wound.
- Minor Adverse Event an undesirable event that did not result in any of the serious- or moderate adverse event outcomes, that is transient and does not lead to permanent disability or mandating prolonged hospitalization, invasive intervention, or prolonged medical treatment. Examples of minor adverse events are post-operative fever that resolved spontaneously, or wound problem that does not mandate drainage or surgical intervention.

Device Relatedness

An assessment regarding the causal relationship between the investigational device and an adverse event (device relatedness) should result in classifying the adverse event as Definitely Related-, Possibly Related-, or Unrelated to the investigational device, as hereby described.

• **Definitely Related** - The adverse event is clearly related to the investigational device, and no alternative cause is present. Such events may be due to device malfunction or direct injury of the device to the surrounding tissue.

- **Possibly Related** There is a reasonable possibility that the adverse event may have been caused by or is linked in a significant way to the investigational device, but an alternative cause is present.
- Unrelated The adverse event is clearly not related to the investigational device, and an alternative cause is present. Such events may be associated with the surgery and general anesthesia or hospitalization, *e.g.*, not related to the anatomic surgical site.

In addition, an independent Clinical Events Committee (CEC) will be established, to review all Adverse Events and determine the following:

- a) Appropriate category for Adverse Events;
- b) Severity, including whether or not the event should be classified as lifethreatening;
- c) Relationship to the device;
- d) Relationship to the procedure.

The CEC will be composed of three members, US orthopedic surgeons, experienced in lumbar spinal fusion and pedicle screws fixation, who had conducted in the past similar clinical studies and similar adverse events evaluations.

All Adverse Events shall be reported to the Sponsor at: [contact]; [contact]; E-mail: [contact]. This shall be done as soon as possible and no later than 5 working days after the event was first discovered. In case of a verbal report, a written notification, using the relevant CRF (Adverse Events Report Form), shall be followed within 5 calendar days.

Serious adverse events, serious adverse device effects, and device deficiencies that could have led to a serious adverse device effects should be reported to the Sponsor within 24 hours after knowledge to the Investigator or any study-related study center staff. Verbal report shall be followed by a detailed written notification within two calendar days, using the relevant form in the CRF.

Language of the reports shall be English.

The Sponsor is responsible for the classification of Adverse Events and ongoing safety evaluation of the clinical investigation, and shall review the Investigator's assessment of all Adverse Events and determine and document in writing their seriousness and relationship to the investigational device.

In case of device deficiency, the Sponsor shall determine and document in writing whether it could have led to a serious adverse device effect.

The Investigator shall supply the Sponsor, upon Sponsor's request, with any additional information related to the safety reporting of a particular event.

The Sponsor shall report to the Institutional Review Board (IRB), or ensure the reporting by the Investigator, of serious adverse events, serious averse device effects, and device deficiencies that could have led to a serious adverse device effect, if required by national regulations or by the IRB/EC. Where required, the Sponsor is responsible for reporting such events to the relevant regulatory authorities.

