The **motor evaluation** measures the muscle strength in major muscle groups (Gluteus Maximus (hip extension); Iliopsoa (hip flexion); Quadriceps (knee extension); Hamstrings (knee flexion); Anterior Tibial Group (ankle dorsiflexion); Extensor Hallucis Longus (great toe extension); Posterior Tibial (ankle plantar flexion/eversion); and Flexor Halluces (great toe flection)). Muscle strength is evaluated on a 6-point scale ranging from 0 to 5 according to the following key

describing the ability of the patient to move the lower extremities against resistance provided by the examiner:

- ▶ 0 no movement;
- ▶ 1- muscle contraction;
- > 2 lateral movement;
- ➤ 3 against gravity;
- ➤ 4 against moderate resistance;
- \blacktriangleright 5 against full resistance.

Light-touch will test **sensation** for all lumbar and sacral dermatomes in comparison to the contralateral site. The sensation shall be graded as equivalent (normal), impaired, absent, as compared to the contralateral side.

Reflexes (Patella and Achilles) are evaluated according to Bate's Reflex Scale (a 5-point scale ranging from 0 to 4) as follows:

- > 0 − no reflex;
- > 1 somewhat diminished, low normal;
- \triangleright 2 average, normal reflex;
- > 3 brisker than average;
- ➤ 4 very brisk, hyperactive.

Straight leg raising is assessed by measurement of the degree of movement required to reproduce symptoms. A positive test is considered when the patient reports worsening of pain between 30 and 70 degrees of hip passive flexion while knee is extended.

Tenderness will be evaluated by palpation of the lower spine area – lumbar paraspinal region, lumber spinous process, sacroiliac joint, and sciatic notch. Tenderness shall be graded as negative or positive (*i.e.*, palpation provokes painful sensation).

 Patient Success –

Individual patient success with respect to *safety* is defined as:

- No worsening in neurological status (motor, sensory, reflex, straight leg raising, and tenderness assessments) and no new permanent neurological deficits present for at least 2 successive visits at or beyond 6 months (out to 24 months);
- Absence of device-related serious adverse events through 24 months;
- Absence of subsequent surgical interventions at the index level through 24 months.

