5.13.4 STATISTICAL ANALYSIS OF DATA

In general, the statistics for numerical variables shall be presented as mean \pm standard deviation, median, minimum and maximum values (range), and sample size (continuous data). Categorical data will be presented as counts (numbers) and percentage of the total (rate). In addition, 95% confidence intervals will be presented for the fusion and adverse events rates. Furthermore, subgroup summary statistics will be calculated where necessary.

Where adequate, comparison between subgroups (*e.g.*, with/without mild stenosis; with/without prior discectomy) shall be presented with differences (*e.g.*, P-values). It should be noted that comparisons between subgroups are supportive analyses; these p-values will not be adjusted for multiplicity.

Adverse events (AE) data will be listed individually and summarized. Overall AE results will be presented both on a per-subject basis and per-event basis (*i.e.*, total number of subjects with each event and total number of events reported).

Results of AE seriousness and device-relatedness will be presented as well.

The report of AEs based on specific type of event will be according to the following AE terms, listed in the table below, and in accordance with FDA list of risks applicable for pedicle screw spinal systems (FDA's Executive Summary, Table 11).

ADEVERSE EVENTS
Implant Malposition
Implant Loosening
Device Breakage
Construct Disassembly
Bone Fracture
Graft Settling/Displacement
Loss of Correction
Pseudoarthrosis
Bleeding/Vascular Injury
Neurologic Injury
Back/Leg Pain (Radiculopathy)
Dural Tear/CSF Leak
Wound problems
Infection/Sepsis
Skin Irritation
Cardiac
Respiratory
Gastrointestinal
Reoperation/Revision
Death

In addition, as per the FDA recommendation, the adverse events will be further analyzed according to the Adverse Events table provided in **Section 5.14.4.2**.

Patients who withdraw from the study (following implantation of the investigational device), are lost to follow-up, or for whom data is missing, will be analyzed individually based on the information already available for the patient. In general, if sufficient data will be available for the patient based on previously gathered

information (*e.g.*, at previous follow-up sessions) or if, in cases where fusion occurs prior to withdrawal and no adverse events have been observed, the patient may be regarded as a success.

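### A death not judged device-related, including one caused by the procedure, enters no success criterion, and no rule says how a deceased patient is counted

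*Combined protocol and SAP*

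**What the plan says.** Individual safety success (5.10.3, repeated in 5.12) has three conditions. The neurological one requires no worsening and "no new permanent neurological deficits present for at least 2 successive visits at or beyond 6 months". The others are "Absence of device-related serious adverse events through 24 months" and "Absence of subsequent surgical interventions at the index level through 24 months". Composite success needs all three plus fusion, pain and function at 24 months.

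Death is a serious adverse event in 5.14.4.1, and the grading in 5.14.4.2 defines a serious event as "an undesirable event that is fatal or life-threatening" or one of several other serious outcomes. Death has a row in the adverse event tables.

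The test for Unrelated in 5.14.4.2 is: "The adverse event is clearly not related to the investigational device, and an alternative cause is present". The text continues: "Such events may be associated with the surgery and general anesthesia or hospitalization", with an example limited to events away from the anatomic surgical site. The Clinical Events Committee (CEC) also determines "Relationship to the procedure" for every event. For the analysis, 5.13.4 says: "Results of AE seriousness and device-relatedness will be presented as well". It does not mention procedure-relatedness.

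The primary population is all treated patients (5.13.3). Section 5.8 does not name death among the reasons for incomplete data, and it carries the last value forward for patients lost to follow-up. Section 5.13.4 handles patients with missing data one by one and allows a success if earlier data are sufficient.

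**The concern.** A patient who dies after implantation stays in the denominator and has to be classified, but no rule says how. The plan separates device harm from procedure harm and lets only the first count against safety. The safety failure rate is set beside a literature figure of 13.5%, so a death from anesthesia or embolism could sit on the success side of that comparison.

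The composite has a related gap. If a patient is fused and improved at 12 months and then dies, someone must decide, with the outcome known, whether the earlier data are sufficient. The composite is judged against a fixed 41%. Even if no number moves, a safety success rate that includes a death caused by the operation is hard to defend.

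**Working it through.** **1. The plan's own safety figure.** From the adverse event table in 5.2.1 D: reoperation/revision 10.9 + neurologic injury 0.8 + screw loosening 0.4 + rod/plate/screw breakage 1.3 + construct disassembly 0.1 = 13.5%. The Wald 95% half-width at N = 100 is 1.96 × √(0.135 × 0.865 / 100) = 6.7 points. Both match 5.12. The sum contains no death term.

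**2. The rules applied to five kinds of death.**

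| Death | Safety component | Composite |
|---|---|---|
| Judged device-related | Fails (device-related serious event) | Fails |
| Operative, remote from the site, graded Unrelated | Meets the stated definition | Normally fails: no fusion result; baseline carried forward gives 0 improvement, below 20 mm and 15 points |
| Operative, at the site, graded Possibly Related | Undetermined: the plan does not say whether this grade counts as device-related | Normally fails, as above |
| Late, unrelated, after fusion and improvement | Meets the stated definition | Can be scored a success (5.13.4; possibly 5.8) |
| Late, unrelated, before fusion or improvement | Meets the stated definition | Fails on the carried-forward values |

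The neurological condition does not close the gap. It looks for deficits at two successive visits from 6 months on, and a patient who died earlier has no such visits.

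**3. Effect on the safety rate.** Each newly counted death adds 1/N. From 13.5%, one death gives 14.5% at N = 100 (13.5 + 1.0) and 15.3% at N = 55 (13.5 + 1.8).

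**4. Effect on the composite.** The documents give no mortality figure, so I assume 0.3-1% over 24 months.

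- Chance of at least one death in 100 patients: 1 − 0.997^100 = 26%; 1 − 0.99^100 = 63%.
- Only a patient who would otherwise be a success changes the composite. With 41% success independent of death, the per-patient probabilities are 0.003 × 0.41 = 0.00123 and 0.01 × 0.41 = 0.0041.
- Chance that at least one composite result changes: 1 − (1 − 0.00123)^100 = 12%; 1 − (1 − 0.0041)^100 = 34%.

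At that success rate these are upper bounds, because early deaths already fail. A true success rate above 41% would raise them, but never beyond the 26-63% for any death at all.

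**5. Effect on the study verdict.** At N = 100 the threshold is 41 successes. One reclassified patient reverses the result only if the count stood at exactly 41, which has a probability of about 8% even when the true rate is 41%.

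**The case against.** A reader might infer that death counts nowhere, that everything caused by surgery is graded Unrelated, and that any patient who dies from the operation is a success. The documents do not support this. A device-related death fails safety. Unrelated requires that the event is clearly not due to the device, and the sentence about surgery is permissive and illustrated by events away from the site. Possibly Related exists for events with another cause but a reasonable device link. The adverse device effect definition in 5.14.4.1 reaches problems of implantation and use error. A perioperative death lacks the fusion, pain and function results that the composite needs.

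Nor is operative harm hidden. The planned table in 5.14.4.2 has intraoperative and perioperative systemic sections and a Death row, and 5.13.4 lists adverse events individually. Only the breakdown of serious events by the CEC's procedure-relatedness is not planned.

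Late deaths are not automatic successes either. Carry-forward is stated for patients lost to follow-up, the 5.13.4 clause is permissive, and one of its two branches requires that no adverse event was observed.

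All of this stands, and it narrows the point without removing it. The Unrelated grade can still hold a remote operative death, the sufficient-data branch of 5.13.4 has no adverse event condition, and no text classifies a deceased patient. It is also fair that the 13.5% has no death term, so adding deaths on the study side alone makes the two rates less alike. The fix has to deal with that.

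**Conclusion.** The gap is real but narrow. Deaths not judged device-related are in no success criterion. A remote operative death graded Unrelated meets the safety definition as written, and a late death after fusion and improvement can be scored an overall success at the analyst's discretion. The status of Possibly Related events is open.

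The numerical effect is at most 1 point per reclassified patient at N = 100. The 12-34% chance that any composite result changes rests on assumed mortality of 0.3-1%, a 41% success rate, and independence of death and success. The 26-63% chance of any death should not be read as the chance of a changed result. The reason to act is that the stated rule gives the wrong answer for a foreseeable event: 5.14.1 lists death among the risks of surgery.

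**What to change.** - **5.10.3 and 5.12:** count a death that the CEC finds device- or procedure-related as a safety failure, and death from any cause before 24 months as a composite failure.
- **5.8 and 5.13.4:** state that no value is carried forward past death and that the discretionary success clause does not apply to deceased patients.
- **5.10.3 or 5.14.4.2:** state whether Possibly Related counts as device-related for the safety criterion.
- **5.13.4:** as a supportive analysis, tabulate serious events by the CEC's procedure-relatedness.

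This takes a few sentences and one table, from determinations the CEC already makes. There are two costs. A death with no link to device or procedure may lower the composite slightly. Because the 13.5% literature rate has no death term, the safety rate should also be shown without the procedure-related deaths for that comparison.
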